### **Table 4**Principles for assessing and reporting abnormal laboratory test results

\*in this situation, this abnormal lab test result is either a manifestation of a concomitant disease or of an already reported AE.

§ grade increase in this context means the value is higher than the one from the screening visit.

In general, laboratory values will be recorded as "increased <lab parameter>" or "decreased <lab parameter>" to ensure consistency of recording/coding.

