# 8.4 Reporting and of Other Events Critical to Safety Evaluation

# 8.4.1 Abnormal Results of Laboratory Tests

Any clinical safety laboratory test result that is outside of the normal reference range will be reviewed by the Investigator and assessed for clinical significance according to its severity. The severity of abnormal laboratory test result must be assessed using CTCAE version 4.03 grading scales (Appendix 3).

Any clinical safety laboratory test result that is outside of the normal reference range will be reviewed by the Investigator and assessed for clinical significance according to its severity. Whenever that grading scheme is not available for the laboratory result of concern, the Investigator should assess the severity and the clinical significance of that result using his/her medical judgment.

Subjects with clinically significant abnormal laboratory values at Screening will not be enrolled. Abnormal laboratory test results detected at the Screening Visit whose CTCAE grades are 2 or higher or still are CTCAE grade 1 and deemed clinically significant are usually

Data and information contained in this document are considered to constitute trade secrets and confidential commercial information, and the legal protections provided to such trade secrets and confidential information are hereby claimed under the provisions of applicable law. No part of this document may be publicly disclosed without the written consent of Philip Morris Products S.A

Philip Morris Products SA	Clinical Study Protocol	Confidential
P1-EXC-01-EU	Version 3.0 / 2 May 2019	Page 78 of 151

concomitant disease or a manifestation of one and must be recorded accordingly. However, in some instances, they may be assessed as AEs (and therefore must be handled according to the directions in Section 8.2) or as manifestations of already reported AEs. This decision will require a careful assessment of the abnormal result within the clinical context on a case-bycase basis and will depend on the Investigator's medical judgment.

Abnormal laboratory test results detected after the screening visit whose CTCAE grades are 2 or higher or still are CTCAE grade 1 and deemed clinically significant must be either recorded as AEs (and handled according to the directions in Section 8.2) or linked to a concomitant disease or still to an already reported AE.

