The principles for assessing and reporting abnormal laboratory test results, emerging after the screening Visit, using CTCAE 4.03 grading scales are set up in Table 4:

Grading	Clinically significant?	ls it a grade increase from previous results in study? §	Report?
Grade 1	No	Not applicable	No
Grade 1	Yes	No	No*
Grade 1	Yes	Yes	Yes, as AE or linked to an already reported AE
Grade 2 or higher	No/Yes	No	No*
Grade 2 or higher	No/Yes	Yes	Yes, as AE or linked to an already reported AE

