### **Confidentiality Statement**

Philip Morris Products SA

P1-EXC-01-EU

Clinical Study Protocol Version 3.0 / 2 May 2019 Confidential

Page 130 of 151

Hematology	Mild (Grade 1)	Moderate (Grade 2)	Severe (Grade 3)	Life- Threatening (Grade 4)
Anemia (Hemoglobin)  (g/dL) (mmol) (g/L)	<lln-10.0 <lln-6.2 <lln-100< td="">< 10-8.0 < 6.2-4.9 < 100-80	<8.0 <4.9 <80 Transfusion indicated	Life threatening consequences; urgent intervention indicated	</lln-100<></lln-6.2 </lln-10.0 	< 10-8.0 < 6.2-4.9 < 100-80	<8.0 <4.9 <80 Transfusion indicated	Life threatening consequences; urgent intervention indicated
Hemoglobin increase  – (g/dL)	Increase in >0 – 2 above ULN or above Baseline if Baseline is above ULN	Increase in >2 – 4 above ULN or above Baseline if Baseline is above ULN	Increase in >4 above ULN or above Baseline if Baseline is above ULN	-
WBC Decrease  - (cell/mm  ) (10  /L)	<lln -="" 3000;
<lln -="" 3.0<="" td=""><3000 - 2000; <3.0 - 2.0	<2000 - 1000; <2.0 - 1.0	<1000; <1.0	</lln></lln>	<3000 - 2000; <3.0 - 2.0	<2000 - 1000; <2.0 - 1.0	<1000; <1.0
Lymphocytes increase  (cell/mm  )	-	>4,000 - 20,000	>20,000	-
Lymphocytes decrease  (cell/mm  ) (10  /L)	<lln -="" 800;
<lln -="" 0.8<="" td=""><800 - 500; <0.8 - 0.5	<500 - 200; <0.5 - 0.2	<200; <0.2	</lln></lln>	<800 - 500; <0.8 - 0.5	<500 - 200; <0.5 - 0.2	<200; <0.2
Neutrophils Decrease  (cell/mm  ) (10  /L)	<lln 1500;
<lln 1.5<="" td="" –=""><1500 - 1000; <1.5 - 1.0	<1000 - 500; <1.0 - 0.5	<500; <0.5	</lln></lln>	<1500 - 1000; <1.5 - 1.0	<1000 - 500; <1.0 - 0.5	<500; <0.5
Platelets decrease  (cell/mm  ) (10  /l)	<lln 75,000;
<lln 75.0<="" td="" –=""><75,000 – 50,000; <75.0 – 50.0	<50,000 – 25,000; <50.0 – 25.0	<25,000; <25.0	</lln></lln>	<75,000 – 50,000; <75.0 – 50.0	<50,000 – 25,000; <50.0 – 25.0	<25,000; <25.0

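### Table 4 in Protocol 8.4.1 defines a laboratory grade increase ambiguously: read literally it misclassifies results that worsen as the value falls, and its comparator differs from the column heading

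*Protocol*

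**What the plan says.** The reporting rule for laboratory abnormalities found after screening appears in several places in Protocol Section 8.4.1.

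- **Text before Table 4.** A result of CTCAE Grade 2 or higher, or Grade 1 and clinically significant, "must be either recorded as AEs (and handled according to the directions in Section 8.2) or linked to a concomitant disease" or to an AE already reported. There is no test of increase and no mention of direction.
- **Table 4, column heading.** The deciding question is whether the result is a "grade increase from previous results in study".
- **Table 4, rows.** For Grade 1 clinically significant results and for Grade 2 or higher, an increase leads to "Yes, as AE or linked to an already reported AE". No increase leads to `No*`.
- **Asterisk.** It explains `No*` by stating that "in this situation, this abnormal lab test result is either a manifestation of a concomitant disease or of an already reported AE".
- **Footnote §.** It defines the deciding term: "grade increase in this context means the value is higher than the one from the screening visit".
- **Sentence after the footnote.** It sets a naming convention that begins "In general, laboratory values will be recorded as" and covers both increased and decreased parameters.

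Appendix 3 gives the grading limits. SAP Section 9.6.4.3 says that the grades are documented in the CRF.

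**The concern.** Grades rise with severity, but measurements do not always. If an investigator takes footnote § at its word and compares measurements, the rule works only for parameters that are harmful when high. For haemoglobin, white cells, neutrophils, lymphocytes, platelets, sodium, potassium, glucose and albumin on the low side, a worsening result is a lower number. It would be classed as no increase.

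The literal reading has support in the section itself. Section 8.4.1 says grade when it means the CTCAE grade, and uses value for the laboratory measurement both in the rule on enrolment after abnormal screening results and in the sentence directly after the footnote.

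The comparator adds a second difficulty, because heading and footnote point to different earlier results.

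Incidence and frequency of AEs are endpoints under Objective 11, and SAP Section 9.6.4.1 tabulates AEs by system organ class and preferred term. Laboratory findings reach those tables only if an investigator reports them. Two investigators reading one footnote differently would feed the tables differently.

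**Working it through.** No figure stated in the plan is at issue, so there is nothing to reproduce. The check applies Table 4 as a decision rule under each reading.

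**1. How many graded rows run downward (Appendix 3)**

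| Panel | Rows | Worsen as the value falls |
|---|---|---|
| Clinical chemistry | 14 | 4 (sodium, potassium, glucose, albumin) |
| Haematology | 7 | 5 (haemoglobin, WBC, lymphocytes, neutrophils, platelets) |
| Urine | 1 | 0 |
| Total | 22 | 9 |

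9/22 = 41%. ALT/AST is counted as one row, and the two directions of a parameter as two rows.

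**2. Direction, with value read as the measurement**

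For a low-direction row, a new abnormality satisfies: value after screening < LLN ≤ screening value. The later value is therefore never higher than the screening value, and Table 4 returns `No*` (for Grade 1, if clinically significant). This holds for any LLN, provided the screening result was not already low.

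In the examples below, the measured values and the LLNs (12 to 13 g/dL for haemoglobin, 1.8 to 2.0 x10^9/L for neutrophils) are assumptions. The grade limits are those of Appendix 3. Results are the same across the LLN ranges.

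| Screening to later visit | Grades | Value = measurement | Value = grade |
|---|---|---|---|
| Haemoglobin 14.0 to 9.0 g/dL | 0 to 2 | `No*` | `Yes` |
| Haemoglobin 14.0 to 7.5 g/dL | 0 to 3 | `No*` | `Yes` |
| Neutrophils 4.0 to 1.2 x10^9/L | 0 to 2 | `No*` | `Yes` |
| Haemoglobin 8.5 to 9.5 g/dL | 2 to 2 | `Yes` | `No*` |

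The last line is a partial recovery that the measurement reading calls an increase. It needs a Grade 2 screening result judged not clinically significant, since 8.4.1 bars enrolment otherwise.

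**3. Against the rest of 8.4.1**

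Under the measurement reading, the first three lines contradict the text before Table 4, which requires recording or linkage. They also make the asterisk untrue, because a new event is neither a concomitant disease nor an AE already reported. Under the grade reading, neither conflict arises in these examples.

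**4. Comparator, with value read as the grade**

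Grades are at V1, V14 and V28, with V3 taken as equal to V1. The decision is the one made at V28.

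| Grades | Against screening (footnote) | Against the latest earlier result | Against the highest earlier result |
|---|---|---|---|
| 0, 0, 2 | `Yes` | `Yes` | `Yes` |
| 0, 2, 2 | `Yes` | `No*` | `No*` |
| 1, 2, 2 | `Yes` | `No*` | `No*` |
| 0, 3, 2 | `Yes` | `No*` | `No*` |
| 2, 1, 2 | `No*` | `Yes` | `No*` |

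In lines two to four, the V14 result was an increase under every comparator and so should already have been reported or linked. At V28, `Yes` can be met by linking to that AE, and `No*` says that the result belongs to it. Neither calls for a new AE.

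The last line differs in substance, and 2, 0, 2 behaves in the same way. The footnote leaves the returning abnormality unreported. The heading, if it means the latest earlier result, calls for an AE or linkage to one.

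**The case against.** The strongest reply is that the grade reading is the natural one. The footnote defines a grade increase, in a column about grade increase, in a table whose first column is the grading. Value may simply be a loose word for the grade. The provision for decreased parameters shows that falls were meant to be recorded. The text before the table requires it independently, and the asterisk cannot truthfully be applied to a new event, so the literal reading defeats itself.

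On the comparator, the footnote expressly defines the heading's term and can be taken to narrow it. Screening is a sensible reference: the subsection on conditions existing before AE collection (numbered 7.1.3 within Section 8) treats unchanged conditions as not AEs and worsened ones as AEs. Most sequences end in the same place under either comparator.

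Laboratory signals would also stay visible. SAP Section 9.6.4.3 lists values with range flags, grades and change from baseline, lists out-of-range values separately, and tabulates counts below, within and above range. Protocol Section 11.2.1 provides for queries on discrepant data.

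Most of this stands, and it limits the consequence. It does not make the footnote correct. The reader must reject the footnote's literal words, which match how 8.4.1 uses value elsewhere, in order to reach the intended rule. The SAP displays keep the laboratory data visible but do not place a finding in the AE tables, and the frequency table of CTCAE grades is optional.

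**Conclusion.** The definition in footnote § is defective as worded, and the point is minor. Read literally, it gives the wrong reporting answer for new abnormalities in 9 of 22 graded rows and conflicts with the text of 8.4.1 and with the convention for decreased parameters. Read as referring to grade, it has no direction problem. The comparator mismatch is real, but it matters in substance mainly when a screening abnormality resolves and returns, and then only if the heading means the most recent earlier result.

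Four stronger conclusions might be inferred, and the documents do not support them.

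- **Sites are told to leave cytopenias unreported.** That follows from one reading only, and the text before Table 4 says the opposite.
- **41% of laboratory AEs would be lost.** The figure counts rows of a grading table, not expected events. The rows are also uneven: hyponatraemia has no Grade 2, and hypokalaemia has the same numeric range for Grades 1 and 2.
- **AE counts would be inflated by stable high values.** A `Yes` can be met by linkage to an AE already reported.
- **Blood sampling of about 235 mL makes missed anaemia likely.** That is a maximum, it includes 80 mL for optional biobanking, and no document ties it to an expected cytopenia.

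The conclusion rests on the wording alone. The worked values are illustrations.

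**What to change.** Bring footnote §, the column heading and the text before Table 4 into line.

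1. Reword the footnote so that a grade increase means a higher CTCAE grade than the comparator, whether the parameter has risen or fallen.
2. Name one comparator and use it in both heading and footnote. Screening and the most recent earlier result are both workable, but they treat a returning screening abnormality differently, so the choice should be deliberate.
3. Check the `Yes` rows against the text. The text also allows linkage to a concomitant disease, which those rows do not mention.

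The cost is one footnote and one heading, with a short clarification to the site. A few more laboratory AEs may be recorded.

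As an optional addition, data management could run a check before database lock for a worsened grade without a matching AE or linked condition, using the grades already in the CRF.

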# 8.4.2 Reporting other abnormal findings

The other abnormal findings (except abnormal results of laboratory tests) discovered during different clinical assessments (e.g., ECG, spirometry, physical examination, vital signs, body weight) should be evaluated for the clinical significance by the Investigator/designee based on

### **Confidentiality Statement**

Philip Morris Products SA	Clinical Study Protocol	Confidential
P1-EXC-01-EU	Version 3.0 / 2 May 2019	Page 79 of 151

his/her medical judgement. All abnormal clinical significant test results or clinical examination findings can, at the discretion of the Investigator, be reported as AEs and handled according to the directions from Section 8.2.

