### **Confidentiality Statement**

Philip Morris Products SA

Clinical Study Protocol

P1-EXC-01-EU

Version 3.0 / 2 May 2019

Confidential

Page 47 of 151

	Exclusion Criteria	Rationale	Screening	Enrollment V2
	neurological, hematological, endocrine, oncological, urological, immunological, pulmonary [such as but not limited to pulmonary oedema, asthma], and cardiovascular [such as, but not limited to myocardial infarction, unstable angina, uncontrolled arrhythmias, heart failure], disease) or any other clinically significant medical condition (including abnormal safety laboratory result as per CTCAE), which as per the judgment of the Investigator would jeopardize the safety of the subject.			
2.	Subject who has forced expiratory volume in 1 second/forced vital capacity (FEV 1 /FVC) <0.7 and FEV 1 <80% predicted value at post-bronchodilator spirometry (GOLD, 2017).	Safety	Х	
3.	Subject with asthma condition (FEV 1 /FVC < $0.75$ and reversibility in FEV 1 (in both > 12% and > 200 mL) from pre to post-bronchodilator values.	Safety	Х	
4.	Subject has clinical significant abnormalities of ECG at V1.	Safety	Х	
5.	Subject performs more than 45 min of vigorous physical activity per week.	Effect	Х	
6.	Inability to perform a VO₂max test at V1.	Safety	Х	
7.	VO 2 max >50 mL.min  kg  for men and VO 2 max >40 mL.min  kg  for women as determined at V1.	Effect	Х	
8.	Subject takes medication influencing blood volume such as erythropoietin, diuretics and beta blockers, or diabetic medications.	Effect	Х	
9.	Subject cannot participate in the study for any reason other than medical as per the Investigator's judgment (e.g. psychological and/or social reason)	Administrative	Х	
10.	For women only: subject is pregnant (does not have negative pregnancy tests at V1 and at V2) or is breastfeeding.	Safety	Х	x

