### 7.11.4 Assessment of Cough-VAS and Likert Scales

Subjects will assess cough on a Visual Analogue Scale (VAS) and on three Likert scales.

Subjects will be asked if they have experienced a regular need to cough (*e.g.*, whether they have coughed several times in the previous 24 hours prior to assessment). If the answer is 'yes', subjects will be asked to complete a VAS and 3 Likert scales. On the VAS, subjects will assess how bothersome their cough was during the previous 24 hours. The VAS ranges from "not bothering me at all" to "extremely bothersome". Furthermore, subjects will assess the intensity and frequency of cough and the amount of sputum production during the previous 24 hours on Likert scales.

- The intensity of cough will be assessed on a 5-point Likert scale ranging from 1 to 5, with 1 = very mild 2 = mild 3 = moderate 4 = severe 5 = very severe.
- The frequency of cough will be assessed on a 5-point Likert scale ranging from 1 to 5, with 1 = rarely 2 = sometimes 3 = fairly often 4 = often 5 = almost always.
- The amount of sputum production will be assessed on a 4-point Likert scale ranging from 0 to 3, with 0 = no sputum 1 = a moderate amount of sputum 2 = a larger amount of sputum 3 = a very large amount of sputum.

Symptoms or worsening of symptoms documented in the VAS do not need to be documented as additional AEs because the VAS will be analyzed as part of the final report. However, it is at the discretion of the Investigator to decide whether to document such symptoms as additional AEs. The main source for AE collection will be the face-to-face interview between the subject and investigational site staff using, open, non-directive questions (see Section 8.2.1).

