# 8 ADVERSE EVENTS

# 8.1 Definitions

# 8.1.1 Adverse Events

An adverse event is defined as any health-related event which is adverse or unfavorable and which either starts after ICF signature or represents a worsening of a health – related condition that existed at the time of that signature. Careful medical judgment is required to establish whether a clinical finding (including an abnormal laboratory result) is a true AE or just a manifestation of a preexisting health – related condition. An AE may or may not have a causal relationship with the study procedures or with the use of investigational product (cigarette or *IQOS*).

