# 8.2 Assessment of Adverse Events

### 8.2.1 Collection of Information

Any non-serious AE occurrence during the study must be documented in the subject's medical records in accordance with the Investigator's normal clinical practice and on the AE page of the CRF. SAEs that occur during the study must be documented in the subject's medical record, on the AE CRF, and on the SAE form.

AEs should be collected mainly via face-to-face interview with the subject through spontaneous reporting or by the use of consistent, open, non-directive questions from the Investigator or designee(s) (e.g., "Have you had any health problems since you were last asked? or "How have you been feeling since you were last asked?").

Information recorded will include: verbatim description of the AE/SAE, start and stop dates, seriousness, severity (intensity), action taken (e.g., whether or not the AE/SAE led to the subject's withdrawal from the study), and outcome (e.g., resolved, stabilized).

Information to be recorded about an SAE should also include, whenever possible, onset and resolution dates and times, circumstances leading up to the event, clinical elements such as clinical course, specific vital signs and test results that may explain the pathophysiology of the event, as well as alternative explanations to its occurrence.

Whenever a medically meaningful diagnosis is available to comprise a set of reported signs and/or symptoms, it should be preferentially provided as the AE or SAE term, rather than the individual signs and/or symptoms. Otherwise, each one of those signs and/or symptoms should be reported separately as event terms.

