9.6.4.4.6 Electrocardiogram

Heart rate (HR), PR, QRS, QT, QTcB, and QTcF intervals will be recorded. Observed values and the changes from baseline will be listed and summarized by study arm and for all study arms (total) and by scheduled time (e.g. visit).

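### Section 8.4.2 makes AE reporting of clinically significant ECG, spirometry, examination, vital-sign and weight findings optional; for new or worsened findings this conflicts with Sections 8.1.1 and 8.2.1, so AE incidence by arm may be incomplete

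*Protocol*

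**What the plan says.** Protocol Section 8.4.2 opens with its scope: "The other abnormal findings (except abnormal results of laboratory tests) discovered during different clinical assessments". It names ECG, spirometry, physical examination, vital signs and body weight as examples, and asks the investigator to assess each abnormal finding for clinical significance. It then states the reporting rule: "All abnormal clinical significant test results or clinical examination findings can, at the discretion of the Investigator, be reported as AEs".

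Three other parts of the protocol bear on the same step:

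- Section 8.1.1 defines an AE as "any health-related event which is adverse or unfavorable and which either starts after ICF signature", or a worsening of a condition present at that time. It also calls for medical judgement on whether a clinical finding is a true AE or only a manifestation of something pre-existing.
- Section 8.2.1 makes documentation a duty: "Any non-serious AE occurrence during the study must be documented in the subject's medical records", and on the AE page of the CRF.
- Section 8.4.1 covers laboratory results after screening. Those of CTCAE grade 2 or higher, or of grade 1 and "deemed clinically significant must be either recorded as AEs", with linkage to a concomitant disease or an already reported AE as the alternative.

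Section 6.5.1 says that site staff are not blinded. SAP 9.6.4.1 reports AE counts and percentages by study arm.

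**The concern.** Section 8.4.2 gives the investigator a choice at a point where the rest of the AE chapter gives none. A finding that is new since consent, adverse and already found clinically significant fits the 8.1.1 definition, and 8.2.1 says it must be documented. A site that follows 8.4.2 to the letter may still leave it off the AE page.

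Two things are at stake. First, AE incidence and frequency are endpoints under Objective 11 and are tabulated by arm. When unblinded staff decide whether to record, the recorded rate can differ between arms for reasons unrelated to the product. Second, a finding that is not recorded as an AE also escapes what follows from AE status: the severity, causality and expectedness assessments (8.2.3 to 8.2.5) and the AE follow-up duty (8.2.6). An asymptomatic ECG change is the clearest case, because an interview about how the subject has been feeling will not bring it out.

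**Working it through.** No figure in the plan depends on this point, so there is none to reproduce. The check is a comparison of the texts.

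**Step 1. Compare the recording rules.**

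| Feature | General AE rule (8.1.1, 8.2.1) | Laboratory rule (8.4.1) | Non-laboratory rule (8.4.2) |
|---|---|---|---|
| Trigger | New, or worse, since consent | Grade 2 or higher, or grade 1 and clinically significant | Abnormal and clinically significant |
| Test for new or worse | Yes | Yes, grade increase since screening (Table 4) | None stated |
| Recording | Mandatory | Mandatory, or link to a concomitant disease or reported AE | Optional |
| Duty to link if not recorded | Not applicable | Yes | None stated |

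The subsection on conditions existing before AE collection (headed 7.1.3, but placed within Section 8.1) points the same way as the general rule. An unchanged pre-existing condition is not an AE; one whose severity has increased is to be captured.

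**Step 2. Ask whether the judgement clause in 8.1.1 explains the discretion in 8.4.2.** It does so in part. The clause concerns whether a finding is a true AE or reflects a pre-existing condition, and that call properly belongs to the investigator. Section 8.4.2 does not limit its discretion to that question. It covers every clinically significant non-laboratory finding, including one the investigator accepts as new. For those findings the two texts cannot both be followed as duties: 8.2.1 requires an entry and 8.4.2 permits none.

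**Step 3. See what the SAP shows if a finding is not recorded as an AE.**

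| Assessment | SAP section | Planned summary | Counts clinical significance? |
|---|---|---|---|
| Physical examination | 9.6.4.4.3 | Frequency of normal, abnormal not significant, and abnormal significant, by arm and time | Yes |
| Vital signs | 9.6.4.4.4 | Values and changes | Not named |
| Spirometry | 9.6.4.4.5 | Values and changes | Not named |
| ECG | 9.6.4.4.6 | "Heart rate (HR), PR, QRS, QT, QTcB, and QTcF intervals will be recorded"; values and changes | Not named |

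For ECG the information is collected. Protocol Section 7.5.7 requires each tracing to be rated normal, abnormal but not relevant, or abnormal and relevant, with a diagnosis on the CRF for the last group. ECGs are taken at V1, V3, V14, V28 and V44 (Protocol Appendix 1). A new rhythm or conduction diagnosis in one subject need not move an arm's mean interval, so the planned ECG summary need not reveal it.

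**Step 4. Size.** Estimating the shortfall would need the rate of clinically significant non-laboratory findings and the fraction left unrecorded, by arm. The documents give neither.

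**The case against.** The strongest reply is that the conflict is narrow and has several backstops, and much of that stands.

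- The definition itself reserves medical judgement to the investigator, so much of the discretion in 8.4.2 is legitimate. This stands for pre-existing conditions. It does not cover a choice to leave out a finding accepted as new.
- SAEs, including important medical events, must be reported within 24 hours (8.1.2, 8.3), and AEs are also elicited by open questions (8.2.1). Both stand. They limit the exposure to non-serious findings, chiefly those without symptoms.
- Laboratory values have CTCAE grades to anchor a mandatory rule, and the protocol gives no such grading for the other assessments. That is a reason to leave the significance call to the investigator, but not a reason to make recording optional once that call has been made.
- Table layouts sit in a separate shell document (SAP Section 1), so an ECG interpretation count may exist there. It can be said only that the SAP text and the title of Table 15.2.3.4.2 do not name one.

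A reader might extend the point to cough, because Section 7.11.4 says: "Symptoms or worsening of symptoms documented in the VAS do not need to be documented as additional AEs". The documents do not support that. The exemption comes with a reason, namely that the VAS is analysed in the final report. The cough questions are put to all arms at the same visits. SAP 9.6.4.4.7 tabulates the VAS, the Likert scales and the number of subjects with and without cough. That is a defensible trade-off.

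A reader might also infer that any clinically significant ECG finding after screening must be new, because an exclusion criterion in Section 5.1.2 reads: "Subject has clinical significant abnormalities of ECG at V1". That does not follow. One resting tracing can miss an intermittent or undiagnosed pre-existing condition, which is the question 8.1.1 leaves to medical judgement.

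**Conclusion.** The point holds as an inconsistency to be reconciled. For clinically significant non-laboratory findings that are new or worse since consent, Section 8.4.2 makes optional what 8.1.1 and 8.2.1 require, and it departs from the mandatory laboratory rule in 8.4.1. Because the choice lies with unblinded staff, AE incidence by arm may be incomplete and may be recorded differently between arms. The gap in the SAP summaries is most practical for ECG, where a diagnosis is collected but no count of clinically relevant tracings is named.

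It would go too far to say that AE rates are incomplete. The documents show that they may be, not that they are. Nor can a size be put on it by dividing one missed subject by 25 or 15: those are randomised arm sizes, while the Safety Set includes enrolled subjects and is analysed by actual exposure (Protocol 12.4.3, SAP 8.2). The study is descriptive with no hypothesis tests, so no formal AE comparison is distorted. The harm would be to the completeness of the safety description.

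The conclusion assumes that sites apply 8.4.2 as written. A site that records every new or worsened significant finding anyway would have no shortfall.

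**What to change.** 1. **Protocol 8.4.2.** Reconcile it with 8.1.1, 8.2.1 and 8.4.1. Clinically significant non-laboratory findings that are new or worse since consent should be recorded as AEs, or linked to a concomitant disease or an already reported AE. Keep the 8.1.1 judgement on whether a finding reflects a pre-existing condition. Leave Section 7.11.4 as it is.
2. **SAP 9.6.4.4.6.** Add a by-arm, by-visit count or shift table of ECG interpretation (normal, abnormal not relevant, abnormal relevant) from V3 to V14, V28 and V44. Confirm first that the three-level rating is on the CRF; Section 7.5.7 expressly places only the diagnosis there. If only the diagnosis is held, a count of subjects with a clinically relevant diagnosis, by arm and visit, would serve.

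The cost is one sentence in the protocol, one more table and slightly higher AE counts. The change does not remove the influence of open-label conduct, because unblinded staff still make the clinical-significance call. It removes only the second, unguided choice that follows it.
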